16.3. Tertiary Immunogenicity

Document: \quintiles.net\Enterprise\Apps\sasdata\SASb\SAS\GlaxoSmithKline\HPV\213749

(HPV9)\Biostatistics\Documentation\SAP\GSK 213749(HPV9-AS04-

001)_WZA97329_SAP_Final_v3.0_02FEB2024.docx

[figure not shown]
Author: PPD Version Number: 3.0

Version Date: 02FEB2024

Template No.: CS_TP_BS016 Revision 7 Reference: CS_WI_BS005

Page 40 of 48

16.4. Sensitivity Immunogenicity Variables & Derivations

Sensitivity analysis will be performed on the PPS only.

Document: \\quintiles.net\Enterprise\Apps\sasdata\SASb\SAS\GlaxoSmithKline\HPV\213749

(HPV9)\Biostatistics\Documentation\SAP\GSK_213749(HPV9-AS04-

001)_WZA97329_SAP_Final_v3.0_02FEB2024.docx

Author: PPD Version Number: 3.0

Version Date: 02FEB2024

Template No.: CS_TP_BS016 Revision 7 Reference: CS_WI_BS005

Effective Date: 01Nov2021

Copyright © 2009, 2010, 2012, 2016, 2018, 2019, 2021 IQVIA. All rights reserved. The contents of this document are confidential and proprietary to IQVIA Holdings Inc. and its subsidiaries. Unauthorized use, disclosure or reproduction is strictly prohibited.

Page 41 of 48

The analysis for anti-HPV IgG antibody concentration (section 16.2.3.1), anti-HPV neutralizing antibody titers between group assessment (section 16.2.4.1), anti-HPV neutralizing antibody titers (section 16.2.3.3), anti-HPV neutralizing antibody titers between group assessment (section 16.2.4.3) and the correlation between anti-HPV IgG antibody concentration and anti-HPV neutralizing antibody titers (section Error! Reference source not found.) will all be performed for the sensitivity analysis. The corresponding figures will also be presented for the sensitivity analysis.

The concentration/titer below the assay cut-off will be assigned to half the cut-off for the purpose of GMC/GMT computation. Concentration/titer above the ULOQ will not be imputed. Concentration below the ULOQ for the RCC will not be imputed for the ECL

17. SAFETY AND REACTOGENICITY OUTCOMES

17.1. Primary Safety and Reactogenicity

17.1.1. Primary Safety and Reactogenicity Variables & Derivations

The primary safety and reactogenicity endpoints are:

- Solicited events:
 - Percentage of participants reporting each solicited administration site event assessed as Grade 3 in terms of intensity within 7 days (Day 1 – Day 7) after each vaccine dose
 - Percentage of participants reporting each solicited systemic event assessed as Grade 3 in terms of intensity within 7 days (Day 1 – Day 7) after each vaccine dose
- Unsolicited adverse events:
 - Percentage of participants reporting unsolicited adverse event assessed as Grade 3 in terms of intensity classified by MedDRA within 28 days (Day 1 – Day 28) after each vaccine dose
- Serious adverse events (SAEs):
 - Percentage of participants reporting SAEs classified by MedDRA from first vaccination up to study end
- Safety laboratory parameters (Step 1 participants):
 - Percentage of participants presenting clinically relevant abnormalities in each biochemical and hematological parameter at Day 7 post-dose 1.

Document: \\quintiles.net\Enterprise\Apps\sasdata\SASb\SAS\GlaxoSmithKline\HPV\213749

(HPV9)\Biostatistics\Documentation\SAP\GSK_213749(HPV9-AS04-

001)_WZA97329_SAP_Final_v3.0_02FEB2024.docx

Author: PPD Version Number: 3.0

Version Date: 02FEB2024

Template No.: CS_TP_BS016 Revision 7 Reference: CS_WI_BS005

Page 42 of 48

17.1.2. Intercurrent Event Handling and Data Imputation for Primary Efficacy Variable(s)

See Table A:.

17.1.3. Primary Analysis of Primary Safety and Reactogenicity Variables

The primary safety and reactogenicity analysis will be performed for the ES.

17.1.3.1. SOLICITED EVENTS

For each study group and overall and each solicited event, the incidence rate (frequencies and percentages) of vaccinated participants with solicited administration site events (pain at injection site, redness at injection site and swelling at injection site) and systemic events (fever, headache, myalgia, arthralgia and fatigue) assessed as Grade 3 in intensity within 7 days after each vaccine administration will be summarized over the whole vaccination course with the exact 95% CI. The number of solicited events will be summarized at the maximum severity per participant. Each solicited event will be counted once regardless of the number of days the event occurred. The percentages will be out of the number of participants in the ES for each period (after first vaccine dose, after second vaccine dose, after third vaccine dose, overall (dose) and overall (participant)) except the overall dose. The overall dose will be out of the total number of doses in the ES.

Intensity scales for solicited events will be assessed as follows:

Adverse Event	MedDRA Preferred Term	Intensity Grade	Parameter
	Administration site pain	1	Mild: Any pain neither interfering with nor preventing normal everyday activities
Pain at Injection Site	(10058049)	2	Moderate: Painful when limb is moved and interferes with everyday activities
		3	Severe: Significant pain at rest. Prevents normal everyday activities.
Redness at Injection	Administration site erythema (10074796)	1	Mild: > 0 - ≤ 20 mm
Site		2	Moderate: > 20 - ≤ 50 mm
		3	Severe: > 50 mm

Document: \\quintiles.net\Enterprise\Apps\sasdata\SASb\SAS\GlaxoSmithKline\HPV\213749

(HPV9)\Biostatistics\Documentation\SAP\GSK 213749(HPV9-AS04-

001)_WZA97329_SAP_Final_v3.0_02FEB2024.docx

Author: PPD Version Number: 3.0

Version Date: 02FEB2024

Template No.: CS_TP_BS016 Revision 7 Reference: CS_WI_BS005

Effective Date: 01Nov2021

Copyright © 2009, 2010, 2012, 2016, 2018, 2019, 2021 IQVIA. All rights reserved. The contents of this document are confidential and proprietary to IQVIA Holdings Inc. and its subsidiaries. Unauthorized use, disclosure or reproduction is strictly prohibited.

Page 43 of 48

Adverse Event	MedDRA Preferred Term	Intensity Grade	Parameter	
Swelling at Injection	Administration site swelling (10075107)	1	Mild: > 0 - ≤ 20 mm	
Site	(10075107)	2	Moderate: $> 20 - \le 50 \text{ mm}$	
		3	Severe: > 50 mm	
	Pyrexia (10037660)	1	Mild: ≥ 37.5°C (≥99.5°F) - ≤ 38.0°C (≥100.4°F)	
Temperature		2	Moderate: > 38.0°C (≥100.4°F) - ≤ 39.0°C (≥102.2°F)	
		3	Severe: > 39.0°C (≥ 102.2°F)	
	Headache (10019211)	1	Mild: Headache that is easily tolerated	
Headache		2	Moderate: Headache that interferes with normal activity	
		3	Severe: Headache that prevents normal activity	
	Fatigue (10016256)	1	Mild: Fatigue that is easily tolerated	
Fatigue		2	Moderate: Fatigue that interferes with normal activity	
		3	Severe: Fatigue that prevents normal activity	
	Arthralgia (10003239)	1	Mild: Arthralgia that is easily tolerated	
Arthralgia		2	Moderate: Arthralgia that interferes with normal activity	
		3	Severe: Arthralgia that prevents normal activity	
	Myalgia (10028411)	1	Mild: Myalgia that is easily tolerated	
Myalgia		2	Moderate: Myalgia that interferes with normal activity	
		3	Severe: Myalgia that prevents normal activity	

Document: \\quintiles.net\Enterprise\Apps\sasdata\SASb\SAS\GlaxoSmithKline\HPV\213749

(HPV9)\Biostatistics\Documentation\SAP\GSK_213749(HPV9-AS04-

001)_WZA97329_SAP_Final_v3.0_02FEB2024.docx

Author: PPD Version Number: 3.0

Version Date: 02FEB2024

Template No.: CS_TP_BS016 Revision 7 Reference: CS_WI_BS005

Page 44 of 48

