2.2. Study Rationale

This project aims at developing a new GlaxoSmithKline Biologicals SA (GSK) AS04-adjuvanted HPV vaccine. The VLP type composition will include HPV types 6, 11, 16, 18, 31, 33, 45, 52, and 58. This study will evaluate the reactogenicity, safety, and immunogenicity of 3 formulations of GSK's investigational adjuvanted HPV vaccine versus *Gardasil 9*, administered intramuscularly (IM) according to a 0, 2, 6 month vaccination schedule in females 16-26 years of age (18-26 years of age in Germany). The aim of the study is to generate data to allow the selection of the investigational adjuvanted HPV vaccine formulation which will be used for the phase 3 studies. Participants who receive the selected formulation and *Gardasil 9* will be invited to participate in an additional 4-year extension study with yearly visits, to generate long-term immunogenicity and safety data.

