9. STATISTICAL CONSIDERATIONS

9.1. Statistical Hypotheses

The primary objective of the study will be evaluated descriptively.

In this study, exploratory immunologic non-inferiority analyses will be performed, to help in decision making of the formulation selection for phase 3.

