9.4.1. Primary Endpoints Analyses

9.4.1.1. Analysis Related to Safety and Reactogenicity

The safety analysis will be based on the Exposed Set (ES).

The percentage of participants reporting each solicited administration site event and systemic event assessed as Grade 3 in intensity during the solicited follow-up period (Day 1 – Day 7 after vaccine administration) will be tabulated, per dose and over the whole vaccination course, with exact 95% CI.

The percentage of participants with at least 1 report of unsolicited AE assessed as Grade 3 in intensity classified by the Medical Dictionary for Regulatory Activities (MedDRA) reported up to 28 days after vaccination will be tabulated with exact 95% CI.

The percentage of participants with at least 1 report of a SAEs classified by MedDRA from first vaccination up to Month 12, will be tabulated with exact 95% CI.

The percentage of participants in Step 1 outside the defined normal ranges for each biochemical and hematological parameter measured in the study at Day 7 post-dose 1 will be tabulated with exact 95% CI.

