17.1.3.3. SERIOUS ADVERSE EVENTS

For each study group and overall, the incidence rates (frequencies and percentages) of participants/events with SAEs from first vaccination up to Month 12 will be summarized by SOC and PT over the whole vaccination course with the exact 95% CI. The incidence rates (frequencies and percentages) of participants with SAEs causally related to study vaccine, fatal SAEs and causally related fatal SAEs occurring post-dose of study interventions will also be presented. Serious AEs will be recorded on the "Expedited Adverse Events" page of the eCRF.

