95% CI = 95% confidence interval computed based on Miettinen and Nurminen method. The concentration below the assay cut-off will be replaced by half the cut-off (LLOQ/2). Concentration above the ULOQ will be replaced by the ULOQ Programming Notes

Document: \\quintiles.net\Enterprise\Apps\sasdata\SASb\SAS\GlaxoSmithKline\HPV\213749 (HPV9)\Biostatistics\Documentation\SAP\Shells\\GSK 213749(HPV9-AS04-001)_WZA97329_TFL Shells_V3.0_05FEB2024.docx

Author: Version Number: 3.0

Table 14.2.2.3: Summary of anti-HPV Neutralizing Antibody GMTs and seropositivity for each antigen at Day 1, Month 2, Month 3 and Month 7 (Per Protocol Set)

GSK Vaccines

Page X of Y

Study 213749 - DELIVERY DESIGNATION

Table 14.2.2.3

Summary of anti-HPV Neutralizing Antibody GMTs and seropositivity for each antigen at Day 1, Month 2, Month 3 and Month 7

Per Protocol Set

	Pre-					
	vaccination					
'isit	status		HPV9 High	HPV9 Medium	HPV9 Low	Gardasil 9
ay 1	Seronegative	N	xxx	xxx	XXX	XXX
-	,	n (%)	xx (xx.x)	xx (xx.x)	xx (xx.x)	xx (xx.x)
		95% CI seropositivity	x.x - x.x	x.x - x.x	x.x - x.x	x.x - x.x
		GMT (GSD)	x.x (x.xx)	x.x (x.xx)	x.x (x.xx)	x.x (x.xx)
		Median	X.X	x.x	x.x	x.x
		Min - Max	x - x	x - x	x - x	x - x
		95% CI GMT	x.x - x.x	x.x - x.x	x.x - x.x	x.x - x.x
	Seropositive	N	XXX	XXX	XXX	xxx
	-	n (%)	xx (xx.x)	xx (xx.x)	xx (xx.x)	xx (xx.x)
		95% CI seropositivity	x.x - x.x	x.x - x.x	x.x - x.x	x.x - x.x
		GMT (GSD)	x.x (x.xx)	x.x (x.xx)	x.x (x.xx)	x.x (x.xx)
		Median	X.X	X.X	x.x	X.X
		Min - Max	x - x	x - x	x - x	x - x
		95% CI GMT	x.x - x.x	x.x - x.x	x.x - x.x	x.x - x.x
		n > ULOQ	xx (xx.x)	xx (xx.x)	xx (xx.x)	xx (xx.x)
	Total	N	xxx	xxx	XXX	xxx
		n (%)	xx (xx.x)	xx (xx.x)	xx (xx.x)	xx (xx.x)
		95% CI seropositivity	x.x - x.x	x.x - x.x	x.x - x.x	x.x - x.x
		GMT (GSD)	x.x (x.xx)	x.x (x.xx)	x.x (x.xx)	x.x (x.xx)
		Median	x.x	x.x	x.x	x.x
		Min - Max	x - x	x - x	x - x	x - x
		95% CI GMT	x.x - x.x	x.x - x.x	x.x - x.x	x.x - x.x
		n > ULOO	xx (xx.x)	xx (xx.x)	xx (xx.x)	xx (xx.x)

Document: \\quintiles.net\Enterprise\Apps\sasdata\SASb\SAS\GlaxoSmithKline\HPV\213749 (HPV9)\Biostatistics\Documentation\SAP\Shells\

GSK 213749(HPV9-AS04-001)_WZA97329_TFL Shells_V3.0_05FEB2024.docx

Author:

Version Number: 3.0

Version Date: 05FEB2024

Table 14.2.2.3

Summary of anti-HPV Neutralizing Antibody GMTs and seropositivity for each antigen at Day 1, Month 2, Month 3 and
Month 7
Per Protocol Set

Visit	Pre- vaccination status		HPV9 High	HPV9 Medium	HPV9 Low	Gardasil 9

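### No between-group difference or interval is planned for any safety endpoint, although the study is meant to assess safety and reactogenicity against Gardasil 9

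*SAP*

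**What the plan says.** Protocol 2.2 states "This study will evaluate the reactogenicity, safety, and immunogenicity of 3 formulations" and goes on to name Gardasil 9 as the comparator. It adds that "The aim of the study is to generate data to allow the selection of the investigational adjuvanted HPV vaccine formulation". The synopsis (Protocol 1.1) uses the same comparative wording. Protocol 9.1 sets the inferential status: "The primary objective of the study will be evaluated descriptively".

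The safety analyses are then written group by group:

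- Protocol 9.4.1.1, Grade 3 solicited events: "will be tabulated, per dose and over the whole vaccination course, with exact 95% CI".
- SAP 17.1.3.1, the same endpoint: "will be summarized over the whole vaccination course with the exact 95% CI".
- SAP 17.1.3.2, Grade 3 unsolicited events: the same form.
- SAP 17.1.3.3, SAEs: "from first vaccination up to Month 12 will be summarized by SOC and PT over the whole vaccination course with the exact 95% CI".

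Shells 14.3.1.1, 14.3.1.2.1, 14.3.1.3.1, 14.3.1.4 and 14.3.1.7 show four group columns and a Total column, with one Clopper-Pearson interval per cell. None has a column for a difference or ratio. The 14.3.2.x safety shells have none either.

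Immunogenicity is treated differently. SAP 16.2.4.1 to 16.2.4.4 plan GMC ratios, GMT ratios and seroconversion differences, both against Gardasil 9 and between formulations. For the seroconversion differences, the footnote to shell Table 14.2.2.2 gives a "95% confidence interval computed based on Miettinen and Nurminen method". SAP 4.3 lists those differences as an addition to the protocol.

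**The concern.** The rationale asks a comparative question about safety and reactogenicity, and the trial has a concurrent randomised comparator that could answer it. The planned output stops one step short: it shows the ingredients of each contrast but neither its size nor its precision.

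Whoever chooses the formulation will have estimated contrasts on immunogenicity and none on Grade 3 reactogenicity. Any safety comparison will then be made informally, by eye from adjacent intervals or by calculations chosen after the data are seen. The safety sizing in Protocol 9.2.1 does not fill the gap, because it describes what one group of 270 can show on its own.

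**Working it through.** **Inputs.** 270 per group (Protocol 9.2). Exact 95% intervals, one per group (Protocol Table 17; shell footnotes). Difference method: Miettinen-Nurminen, two-sided 95% (shell 14.2.2.2). An illustrative Grade 3 rate of 10% (Protocol 9.2.1). The documents give no expected rate by group, so the other rates below are assumptions.

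**1. The plan's own figures reproduce.** Chance of at least one event in 270 at a 1.0% rate: 1 − 0.99^270 = 0.934, against the stated 93% or more. All eight rows of Table 17 match the Clopper-Pearson limits to 0.1 point. Both are single-group properties.

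**2. Two rows of Table 17 set against each other.** Treat 50/270 and 30/270 as two groups.

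- Single-group intervals: 14.1% to 23.7% and 7.6% to 15.5%. They overlap between 14.1% and 15.5%.
- Difference: (50 − 30)/270 = 7.4 points.
- Score statistic: T(d) = (p1 − p2 − d)/√v, where v = [(q+d)(1−q−d)/n1 + q(1−q)/n2] × (n1+n2)/(n1+n2−1) and q is the restricted estimate of p2 given d.
- At d = 0, q = 80/540 = 0.1481 and v = 0.1481 × 0.8519 × (2/270) × (540/539) = 0.000937, so T = 0.0741/0.0306 = 2.42, beyond 1.96.
- Solving T(d) = ±1.96 gives a 95% CI of 1.4 to 13.5 points.

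A second pair, 27/270 and 10/270, has intervals 6.69% to 14.22% and 1.79% to 6.71%, which just overlap. The difference is 17/270 = 6.3 points, 95% CI 2.1 to 10.9.

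**3. How far the two readings differ in general.** Exact enumeration over two independent binomial counts with n = 270 each:

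| Assumed true rates | Difference CI excludes 0 | Two exact CIs do not overlap |
|---|---|---|
| 10% vs 5% | 61% | 23% |
| 20% vs 10% | 91% | 66% |
| 37% vs 25% | 86% | 56% |
| 10% vs 10% | 5.0% | 0.4% |

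Read by overlap, the planned intervals act like a test at about 0.4%, not 5%.

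**4. Precision available.** With 27/270 in both groups, the Miettinen-Nurminen interval for the difference is −5.2 to +5.2 points. The trial can therefore say something useful about common Grade 3 events, though little about rare ones.

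**The case against.** The strongest reply is that the plan does what it declares. Protocol 9.1 makes the primary objective descriptive. SAP Table A defines the summary for each primary safety endpoint as a percentage with its exact interval, and the primary safety objective names no comparator. Protocol 4.2.1 gives the comparator's purpose as comparing immunologic profiles, and Protocol 9.1, 9.2.2.1 and 9.4.2.2.2 tie formulation selection to immunologic analyses. All of that stands, and it makes this a disclosed choice rather than a contradiction. It does not remove the comparative wording in Protocol 1.1 and 2.2. A descriptive status rules out a confirmatory claim, not an effect estimate: the non-inferiority analyses are exploratory too and still report ratios with intervals.

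Several stronger readings are tempting but unsupported:

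- A reader might infer that the groups are never compared on safety. The shells put all four side by side with counts and denominators. The iSRC also sees unblinded safety data under a separate plan that is not among these documents.
- A reader might infer that results must be judged by overlap of intervals. No section says so. Step 3 measures a habit that the layout invites, not a rule in the plan.
- A reader might call the safety endpoints co-primary. There are two primary objectives and no joint success rule.
- A reader might infer a selection rule that trades immunogenicity against Grade 3 reactogenicity. None is stated.
- A reader might call these strictly randomised contrasts. The Exposed Set groups participants by vaccine administered (SAP 6.3).

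The objection about volume also stands. Shells 14.3.1.1, 14.3.1.2.1, 14.3.1.3.1 and 14.3.1.4 have 3 + 8 + 12 + 6 = 29 rows. Six contrasts over four periods would give 29 × 6 × 4 = 696 intervals, of which up to about 0.05 × 696 ≈ 35 could exclude zero with no true difference. Any addition has to be short.

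**Conclusion.** The point holds as a cheap improvement, not as an error. The plan provides no estimate or interval for any safety contrast, although its stated rationale is comparative and the SAP already specifies a suitable method for another binary endpoint.

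The size of the gap is shown by the protocol's own Table 17: a 7.4-point difference with a CI of 1.4 to 13.5 sits behind two overlapping intervals. That example and the limits are exact for those counts. The percentages in step 3 rest on assumed rates, 270 analysed per group and a reader who judges by overlap, so they illustrate the risk rather than predict it. Nothing here affects the validity of the within-group percentages and intervals, which should stay.

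**What to change.** In SAP 17.1.3.1 to 17.1.3.3 and the matching shells, add the difference in percentage with a two-sided 95% Miettinen-Nurminen CI, in the layout of shell 14.2.2.2, for overall (participant) rows only:

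- **Each HPV9 group minus Gardasil 9:** any Grade 3 solicited administration-site event, any Grade 3 solicited systemic event, each of the eight Grade 3 solicited events, any Grade 3 unsolicited AE, and any SAE. That is 12 rows × 3 contrasts = 36 intervals.
- **Between formulations:** the three any-Grade-3 rows only, 3 × 3 = 9 intervals.

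Label the intervals descriptive and by vaccine administered, with no p-values and no multiplicity claim. Do not extend them to SOC or PT rows. Keep the within-group exact intervals and list the addition in SAP 4.3.

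The cost is SAP and shell wording plus re-use of the seroconversion-difference program, with no new data, visits or participants. The downside is 45 unadjusted intervals. At the nominal 5%, about 0.05 × 45 ≈ 2 could exclude zero by chance, fewer where events are rare, which is why the label matters.

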17.1.3.2. Unsolicited Events

For each study group and overall, the incidence rates (frequencies and percentages) of participants/events with unsolicited AEs, assessed as Grade 3 and Grade 3 related in intensity assessed by MedDRA occurring within 28-days (Days 1-28) after each vaccine administration will be summarized by SOC and PT over the whole vaccination course with the exact 95% CI. The percentages will be out of the number of participants in the ES for each vaccine dose (after first vaccine dose, after second vaccine dose, after third vaccine dose, overall (dose) and overall (participant) expect the overall dose. The overall dose will be out of the total number of doses in the ES.

Unsolicited events will be coded using MedDRA central coding dictionary, version 26.0 or higher. Unsolicited events will be described using frequency and percentage.

Unsolicited events will be grouped by SOC and PT and summarized by intervention at time of onset of the event. The summary tables will present the number and percentage of total participants and number of events, by SOC and by PT for each intervention group.

For the summaries of unsolicited events, participants who experience the same AE (in terms of the MedDRA SOC and PT) more than once will only be counted once for that event in the number of participants but all occurrences of the same event will be counted in the number of events.

17.1.3.3. SERIOUS ADVERSE EVENTS

For each study group and overall, the incidence rates (frequencies and percentages) of participants/events with SAEs from first vaccination up to Month 12 will be summarized by SOC and PT over the whole vaccination course with the exact 95% CI. The incidence rates (frequencies and percentages) of participants with SAEs causally related to study vaccine, fatal SAEs and causally related fatal SAEs occurring post-dose of study interventions will also be presented. Serious AEs will be recorded on the "Expedited Adverse Events" page of the eCRF.

17.1.3.4. LABORATORY PARAMETERS OUTSIDE NORMAL RANGE

For each study group and overall, the percentage of participants in Step 1 outside the defined normal ranges for each biochemical and hematological parameter measured in the study at Day 7 after the first vaccination will be tabulated with exact 95% CI.

Document: \\quintiles.net\Enterprise\Apps\sasdata\SASb\SAS\GlaxoSmithKline\HPV\213749

(HPV9)\Biostatistics\Documentation\SAP\GSK_213749(HPV9-AS04-

001)_WZA97329_SAP_Final_v3.0_02FEB2024.docx

Author: PPD Version Number: 3.0

Version Date: 02FEB2024

Template No.: CS_TP_BS016 Revision 7 Reference: CS_WI_BS005

Page 45 of 48

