Recording of all SAEs, including SAEs related to study intervention, to study participation, to a concurrent GSK medication/vaccine ⁴	•	•	•	•	•	•	•	
Recording of AEs/SAEs leading to withdrawal of a participant from the intervention/study	•	•	•	•	•	•	•	
Recording of pregnancies and pregnancy outcomes ⁵	•	•	•	•	•	•	•	
Recording of pIMDs	•	•	•	•	•	•	•	See Table 21
Study Conclusion							•	See Section 4.3

(the table footnote continues on the next page)

* 18-26 years of age for Step 1 participants.

Note: In Germany, only adult participants between and including 18 to 26 years of age are to be included in this clinical study

** For Step 1 participants only

AE = adverse event; D = day; eDiary = electronic diary; LAR = legally authorized representative; pIMD = potential immune-mediated disease; SAE = serious adverse event

- is used to indicate a study procedure that requires documentation in the individual electronic case report form (eCRF)
- o is used to indicate a study procedure that does not require documentation in the individual eCRF
- The preferred location for measuring the temperature is the axilla. Fever is defined as body temperature ≥37.5°C/99.5°F.
- Blood samples should be collected prior to vaccine administration.
- Only for 200 participants (50/group) at pre-selected sites.
- The collection and reporting period starts once the participants' informed consent (and assent, if applicable) is obtained.
- ⁵ Follow-up of pregnancy outcomes will be done beyond Month 12.

Table 2 Intervals Between Study Visits

Interval	Planned Visit Interval*	Allowed Interval Range
Visit 1→Visit 2**	7 days	7 – 12 days
Visit 1→Visit 3	60 days	56 – 74 days
Visit 3→Visit 4	28 days	28 – 44 days
Visit 1→Visit 5	180 days	166 – 194 days
Visit 5→Visit 6	28 days	28 – 44 days
Visit 1→Visit 7	360 days	346 – 374 days

^{*}Number of days between the visits.

^{**}Visit 2 is for Step 1 participants only.

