2.3.3. Overall Benefit/Risk Conclusion

The investigational adjuvanted HPV vaccine is currently in an early stage of clinical development and no vaccine efficacy has been demonstrated in humans. Taking into account the measures to minimize the risk to the participants, the potential risks are justified by the potential benefits linked to the development of this investigational adjuvanted HPV vaccine.

3. Objectives and Endpoints

Table 4 Study Objectives and Endpoints

	Objectives	Endpoints
	Prin	nary
•	To evaluate the safety and reactogenicity of GlaxoSmithKline Biologicals SA (GSK)'s investigational adjuvanted human papillomavirus (HPV) vaccine formulations.	Percentage of participants reporting each solicited administration site event assessed as Grade 3 in terms of intensity within 7 days (Day 1 – Day 7) after each vaccine dose.
		 Percentage of participants reporting each solicited systemic event assessed as Grade 3 in terms of intensity within 7 days (Day 1 – Day 7) after each vaccine dose.
		Unsolicited adverse events (AEs)
		 Percentage of participants reporting unsolicited adverse event assessed as Grade 3 in terms of intensity classified by Medical Dictionary for Regulatory Activities (MedDRA) within 28 days (Day 1 – Day 28) after each vaccine dose.
		Serious adverse events (SAEs)
		 Percentage of participants reporting SAEs classified by MedDRA from first vaccination up to study end.
		Safety laboratory parameters (Step 1 participants)
		 Percentage of participants presenting clinically relevant abnormalities in each biochemical and hematological parameter at Day 7 post-dose 1.
•	To evaluate the immune response to GSK's investigational adjuvanted HPV vaccine formulations.	• Anti-HPV immunoglobulin G (IgG) antibody geometric mean concentrations (GMCs), 1 month after the third dose (Month 7).
	Secon	ndary
•	To evaluate the safety and reactogenicity of GSK's	Solicited events
	investigational adjuvanted HPV vaccine formulations.	 Percentage of participants reporting each solicited administration site event within 7 days (Day 1 – Day 7) after each vaccine dose.
		 Percentage of participants reporting each solicited systemic event within 7 days (Day 1 – Day 7) after each vaccine dose.
		Unsolicited AEs
		 Percentage of participants reporting unsolicited symptoms within 28 days (Day 1 – Day 28) after each vaccine dose.
		Potential immune-mediated disease (pIMDs)
		 Percentage of participants reporting pIMDs from first vaccination up to study end.

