Blood sample collection:

- A 5 mL blood sample will be drawn from Step 1 (Sentinel) participants at Visit 1 (Day 1) and Visit 2 (Day 7) to assess biochemical and hematological parameters.
- For assessment of immune response, blood samples (~50 mL) will be drawn at Day 1, Month 2, Month 3, Month 6, Month 7 and Month 12 in all participants. Immunoglobulin G (IgG) antibody determination will be performed for these timepoints in all participants. Pseudovirion-based neutralization assays will be performed. Blood samples drawn at Day 1 (all participants), Month 2 (at least 96 participants in each group), Month 3 (all participants) and Month 7 (at least 150 participants in each group) will be tested.

Study	Number of	Number of Age	Study	Blinding*	
groups	participants	(Min-Max)	vaccinations	Visit 1 to Visit 7 (Observer- Blind)	
HPV9High	270	16-26 years of age	HPV9-High	X	
HPV9Med	270	16-26 years of age	HPV9-Medium	X	
HPV9Low	270	16-26 years of age	HPV9-Low	X	
Gar9	270	16-26 years of age	Gardasil 9	X	

Table 5 Study Groups, Vaccines, and Blinding

Note: In Germany, only adult participants between and including 18 to 26 years of age will be included in this clinical study.

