5.3. Screen Failures

Not applicable as there is no screening phase of the potential participants as part of this study.

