17.3. Laboratory Parameters

Scheduled clinical safety laboratory parameters will be summarized at each visit by grade (grade 0, 1, 2, 3 and 4) according to Table 13 of the protocol. These include:

- Hematology: hemoglobin, hemoglobin change from baseline, White Blood Cell (WBC) increase, WBC decrease, lymphocyte decrease, neutrophils decrease, eosinophils and platelet decrease
- Chemistry: Blood Urea Nitrogen (BUN), Aspartate Aminotransferase (AST) and Alanine Aminotransferase (ALT)

Box plots of the above summary will be presented for the iSRC analysis.

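### The primary Day 7 laboratory percentage mixes abnormalities present before vaccination with new ones, because it is not compared with each woman's own Visit 1 sample

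*SAP*

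**What the plan says.** The endpoint in Protocol Section 3 (Table 4) is the "Percentage of participants presenting clinically relevant abnormalities in each biochemical and hematological parameter at Day 7 post-dose 1", and SAP 17.1.1 repeats it. Baseline is not mentioned. The analysis rule in SAP 17.1.3.4 is the "percentage of participants in Step 1 outside the defined normal ranges for each biochemical and hematological parameter" at Day 7, by group and overall, with an exact 95% CI. Protocol 9.4.1.1 is almost identical. Shell Table 14.3.1.11 has one Day 7 count per parameter, with no Visit 1 result, no restriction to women in range at Visit 1, and no new-or-worsened rule.

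The baseline data exist. Protocol 4.1 takes a 5 mL safety sample from Step 1 women at Visit 1 and Visit 2, and a footnote to the schedule of activities says "Blood samples should be collected prior to vaccine administration".

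Visit 1 results appear in three other places:
- SAP 17.3: "Scheduled clinical safety laboratory parameters will be summarized at each visit by grade", which Tables 14.3.3.1 and 14.3.3.2 show as separate counts for Visits 1 and 2.
- Hemoglobin change from baseline, within that same summary.
- Listing 16.2.8.1, which gives each participant's results, reference range, investigator assessment and grade.

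On eligibility, Protocol 5.3 states that "there is no screening phase of the potential participants as part of this study". Exclusion 11 (Protocol 5.2.1) bars clinically significant pulmonary, cardiovascular, neurologic, hepatic or renal abnormality found on examination or laboratory tests.

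**The concern.** The objective is vaccine safety, and a reader will take the Day 7 percentage as a measure of what happened after the dose. As written, it measures how many women are out of range at Day 7 for any reason, including long-standing mild deviations. With no screening phase, and with sampling, randomization and dose 1 all at Visit 1, nothing in the plan removes such women in advance.

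The by-visit grade tables do not solve this. They are marginal counts: one woman resolving while another becomes abnormal looks the same as no change in either. Apart from hemoglobin change, no planned summary table pairs a woman's two results.

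With 12 women per group, each carried-over case moves a parameter's percentage by 1/12 = 8.3 points.

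**Working it through.** **Inputs from the documents.** Step 1 has 48 women, 12 per group (Protocol 9.2), randomized 1:1:1:1 (Protocol 6.3.2). Protocol Table 10 lists 12 analytes: 9 hematology and 3 biochemistry. Table 13 grades 9 of the 12; erythrocytes, monocytes and basophils have no grades.

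**Assumed, because the documents give no values.** Out-of-range prevalence b per parameter, with no vaccine effect, is 5% (range 2.5% to 20%). Visit 1 and Day 7 values are bivariate normal with correlation 0.5, 0.7 or 0.9.

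**The plan's own Step 1 figure.** Protocol 9.2.1 states at least 80% probability of seeing one or more AEs among 12 at a true rate of 12.6%. Check: 1 − (1 − 0.126)^12 = 0.801, so it reproduces. The plan gives no figure for the laboratory endpoint.

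**Background at Day 7 with no vaccine effect.**
- At least one case in a group of 12, per parameter: 1 − (1 − b)^12 = 26%, 46%, 72% and 93% for b = 2.5%, 5%, 10% and 20%.
- Out-of-range results across Step 1 at b = 5%: 48 × 12 × 0.05 = 28.8.
- One woman in 12 reads as 8.3% (exact 95% CI 0.2% to 38.5%); two read as 16.7% (2.1% to 48.4%).

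**How much of this is carry-over.** Let s be the probability that a woman out of range at Day 7 was out on the same side at Visit 1. With cut-offs at ±1.96, s is the bivariate normal probability that both values lie beyond the same cut-off, divided by 0.025. The rate of cases that are not carry-over is 0.05 × (1 − s). The SD of the difference between two groups' counts at rate p is √(2 × 12 × p × (1 − p)).

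| | Correlation 0.5 | 0.7 | 0.9 |
|---|---|---|---|
| s | 18% | 33% | 59% |
| Rate excluding carry-over | 4.1% | 3.3% | 2.0% |
| Expected per 12 women (0.60 as planned) | 0.49 | 0.40 | 0.24 |
| Chance of at least one per 12 (46% as planned) | 39% | 34% | 22% |
| SD of count difference (1.07 as planned) | 0.97 | 0.88 | 0.69 |

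Pairing thus lowers both the reported level and the noise in the contrast. It does not remove chance new abnormalities. The table leaves out carried-over cases that worsen in grade, which would rejoin the new row.

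**Between-group contrast.** Carry-over has the same expectation in all four groups, so it adds no systematic difference. Chance differences are still likely. For one parameter, the probability that at least one HPV9 group exceeds Gardasil 9 by two or more women with no vaccine effect is 19%, 33% and 43% for b = 5%, 10% and 20%. These figures are for total background, of which carry-over is one part.

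**The case against.** Several points on the other side stand.

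- **Direction.** A reader might infer that prior abnormalities count against the investigational vaccine. The documents do not support that: the Gardasil 9 group is randomized concurrently, counted by the same rule and shown in the same table, and the analysis is descriptive. Each group's level is inflated as a measure of new abnormality; the contrast is not tilted.
- **Visit 1 is not ignored throughout.** Listing 16.2.8.1 would let a reader pair results by hand for 48 women. Appendix 4 of the protocol makes a laboratory finding present at baseline an AE if it significantly worsens. Holding rule 2c requires onset within Days 1 to 7. A reader might infer that the sentinel safety decision rests on the Day 7 table; it does not.
- **Eligibility.** Protocol Section 8 requires eligibility results to be reviewed before eligibility is confirmed, and exclusion 11 mentions laboratory tests. This may remove some clinically significant organ abnormality. But no text makes the Visit 1 safety panel an eligibility test, exclusion 11 names no hematological abnormality, and mild out-of-range values would pass. It would be too strong to say that eligibility removes nothing.
- **Size.** The 46% is total background in 12 women, not carry-over, and prevalence and correlation are assumed. The figures apply to the out-of-range rule; no size can be given for clinically relevant abnormalities, which the health and exclusion criteria should make rarer.

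What remains is that the primary percentage cannot separate pre-existing from new abnormality, and no planned summary table does so except for hemoglobin change.

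**Conclusion.** The point holds as a limitation of what the primary laboratory percentage measures. Followed as written, Protocol 9.4.1.1, SAP 17.1.3.4 and Table 14.3.1.11 report Day 7 prevalence, which overstates new abnormality in every group. The comparison with Gardasil 9 is made noisier, not biased.

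Under the assumptions above (5% prevalence, no vaccine effect, correlation 0.5 to 0.9), between about one fifth and three fifths of Day 7 cases would be carry-over. The true share depends on local reference ranges and the women enrolled, which the documents do not describe. That carried-over cases are counted follows from the text alone. The change is worth making because the table serves a primary safety endpoint and the paired data are already in hand.

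**What to change.** 1. Keep the protocol-specified Day 7 out-of-range row in Table 14.3.1.11.
2. Beside it, add the number and percentage (exact 95% CI) of Step 1 women with both samples whose Day 7 abnormality is new or worse in grade than at Visit 1. For erythrocytes, monocytes and basophils, which Table 13 does not grade, count women newly out of range.
3. Add a Visit 1 to Visit 2 grade shift table to 14.3.3.1 and 14.3.3.2.
4. Describe the new row in SAP 17.1.3.4 and record the additions in SAP 4.3, since the protocol specifies only the Day 7 row.

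The cost is slightly more output and programming. No new samples, visits or participants are needed. Women without a Visit 1 result drop out of the new row only.
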